12.0 ADVERSE EVENT REPORTING

12.1 Definition

Adverse event: Any unfavorable and unintended sign (including abnormal laboratory finding), symptom, or disease temporally associated with the use of a medical treatment or procedure, regardless of whether it is considered related to the medical treatment or procedure; also an "unanticipated problem" of any nature (e.g., psychological or social harm) (designated as unrelated, definitely related, probably related, or possibly related; see below)

Serious adverse event: Any adverse event that is fatal or life threatening, is permanently disabling, requires inpatient hospitalization or prolongs hospitalization, or results in a congenital anomaly or birth defect

Life-threatening event: Any adverse event in which the subject is at immediate risk of death from the reaction as it occurs; does not include a reaction that, if it were to occur in a more serious form, might cause death

Unexpected event: Any adverse event that is not identified in nature, severity, or frequency in the investigator brochure, study protocol, consent form, or IND application; or the event was more serious than anticipated

Association:

Definitely Related: An adverse event that has a timely relationship to the administration of the investigational drug/study procedure and follows a known pattern of response which no alternative cause is present

Probably Related: An adverse event that has a timely relationship to the administration the investigational drug/study procedure and follows a known pattern of response, but which a potential alternative cause may be present

Possibly Related: An adverse event that has a timely relationship to the administration the investigational drug/study procedure, follows no known pattern of response, potential alternative cause does not exist

Unrelated: An adverse event for which there is evidence that it is definitely a related cause other than the investigational drug/agent; in general, no timely relationship administration of the drug/procedure exists, or if so, the event does not follow a pattern response and an alternative cause is present

The Common Terminology Criteria for Adverse Events v4.0 (CTCAE) of the National Cancer Institute will be used. The severity of adverse reactions is categorized as grade 1 to grade 5 in increasing severity. Grade 3, 4 and 5 toxicities will be reported as adverse events. General descriptors for the toxicity grades range from mild to fatal:

Grade 1 – Mild (The adverse reaction does not interfere in a significant manner with the subject's normal functioning level. It may be an annoyance.)

Grade 2 – Moderate (The adverse reaction produces some impairment of functioning but is not hazardous to health. It is uncomfortable and/or an embarrassment)

Grade 3 - Severe (The adverse reaction produces significant impairment of functioning or incapacitation and is a definite hazard to the subject's health)

Grade 4 – Adverse reactions that include or lead to either a) a life-threatening event, though acute and without permanent effect, b) prolonged inability to resume usual life pattern, or c) impairment of ability to adequately deal with future medical problems

Grade 5 – Fatal

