11 POTENTIAL RISKS AND MANAGEMENT

Because we will be obtaining information about a participant's medical history, lifestyle behaviors, and measuring biomarkers that will become part of the electronic health record, there is a chance that we will uncover or discover sensitive information regarding a person's health status. Although unlikely, this information could cause emotional distress, increase personal expense for treatment, or, if obtained by insurance companies or employers, could be used as justification to raise insurance rates or affect employability. To ensure privacy/confidentiality, information that is received from patients will be kept confidential to the extent allowed by law. Patient data will be entered into the electronic health record and hard copies will be kept in a secure filing cabinet on site for the duration of the study. We will assign all patients a code number to be used on forms, sample collection containers and other research materials. Subject codes will be employed for database management and when statistical analyses are performed. There will be a single key to the coded data kept on a password protected computer. Computer files containing names, addresses or other identifiers will be limited to authorized personnel at the site who have access to the computer data base using a password protected program. All investigators, professional medical staff, and technicians are aware of the confidentiality involved with the proper conduct of such a study. Consistent with the conduct of human research studies, the data will not be available or divulged to anyone outside of the experimental research team. The results from the study may be published, but will have no identifiers.

Radiation Treatment. Possible Side Effects of Radiosurgery (Radiation)

	COMMON, SOME MAY BE SERIOUS
	In 100 people receiving radiation therapy, 20 to 100 may have:
•	If a head frame is used, temporary (short-term) pain from the
	head frame placement

OCCASIONAL, SOME MAY BE SERIOUS

In 100 people receiving radiation therapy, 4 to 20 may have:

- Headache
- Tiredness
- If a head frame is used, bleeding and/or infection around the head frame pin sites

RARE, SOME MAY BE SERIOUS

In 100 people receiving radiation therapy, 3 or fewer may have:

- Nausea
- Reddening of the skin
- Localized hair loss which may be permanent

RARE, AND SERIOUS				
	In 100 people receiving radiation therapy, 3 or fewer may have:			

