•	Decreased brain function such as motor function (coordination/movement)			
•	Swelling of the brain in the treated area which may require steroids			
•	Severe local damage to or death of normal brain tissue, which may require surgery to remove			
•	Seizure			

Ketogenic Diet. There are no significant risks associated with consuming a well-formulated ketogenic diet. For patients using medication to control blood sugar and blood pressure, there is a need to reduce these medications rather quickly at the onset of the diet to prevent low blood sugar and hypotension. In this study, we will exclude those patients who have type-2 diabetes using insulin. In our prior research we have assessed thousands of metabolic panels in patients assigned to ketogenic diets. Abnormal responses are rare, but it is expected that there will be modest changes in some metabolic parameters. These markers are expected to remain within normal limits and not pose a serious concern. For example, uric acid levels often increase during the first few weeks of a ketogenic diet and then return to or below baseline after 1-2 months. This transient increase does not exacerbate gout or have other untoward effects, since the elevation is due to competition with ketones for renal excretion, in contrast to increased intracellular synthesis of uric acid. Nutritional ketosis is associated with natriuresis (increased loss of sodium in the urine) and fluid loss. If the extra sodium excreted is not compensated for in the diet, the subsequent contracted plasma volume can manifest in side effects and adrenal stress including a hormonal response that disrupts body mineral status. Our diets contain adequate sodium and potassium to ensure mineral nutriture. The diet intervention may be challenging for participants since it will require them to limit foods, they are accustomed to eating. Participants will be made aware of the general dietary requirements including lists of foods they will need to restrict (as well as foods that will be permitted) during the informational session, so they can make an educated decision to participate.

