12.3 Reporting

According to FDA regulations (21 CFR 312.32), IND safety reports shall address "any adverse

experience associated with the use of a drug that is both serious and unexpected." The IRB will be notified of any adverse event fulfilling the following criteria:

12.3.1 The adverse event is **SERIOUS** (as defined above),

or

12.3.2 The adverse event is not serious, but is **UNEXPECTED** and its association with the study drug, device, or research-related procedure is either **DEFINITELY**, **PROBABLY**, or **POSSIBLY RELATED**, or **UNKNOWN** (as defined above).

Federal policy [45 CFR 46.116(b)(5)] also requires that investigators inform subjects of any important new information that might affect their willingness to continue participating in the research. When an adverse event necessitates changes to the consent/assent form(s) and/or protocol, or that notification is given to currently or previously enrolled subjects, an amendment request will be submitted in conjunction with the adverse event report. The IRB will make a determination whether any new findings, new knowledge, or adverse effects should be communicated to subjects.

In accordance with IRB guidelines, serious adverse events will be reported within 10 days of learning of the event to the Office of Research Risks Protection, [name], CAMPUS, [contact] telephone, [name] fax, Email: [contact], using the Event Reporting Form (http://orrp.osu.edu/irb/event/documents/EventReportingForm v2.2.doc) of The Ohio State University Institutional Review Boards. If the adverse event involved the death of a subject, it will be reported immediately, usually within 72 hours. Deaths from "natural causes" or underlying disease that occur more than 30 days following completion of study interventions (i.e., events not temporally associated) need not be reported. Unexpected adverse events that are not serious but may be associated with the drug, device, or procedure (see below) should generally be reported to the IRB within 30 days of notification of the event.

In some instances, adverse events or "unanticipated problems" result in social or psychological harm rather than physical harm to subjects or others. These events should also be reported to the IRB within 30 days, unless they are considered "serious". A letter format may be used for reporting these events instead of the Event Reporting Form, as applicable.

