16.7 Data Safety Monitoring Plan

The data and safety monitoring plan will involve the continuous evaluation of safety, data quality and data timeliness. Investigators will conduct continuous review of data and patient safety at their regular Disease Group meetings (at least monthly) and the discussion will be documented in the minutes. The Co-PIs of the trial will review toxicities and responses of the trial where applicable at these disease center meetings and determine if the risk/benefit ratio of the trial changes. Frequency and severity of adverse events will be reviewed by the Co-PIs and compared to what is known about the agent/device from other sources; including published literature, scientific meetings and discussions with the sponsors, to determine if the trial should be terminated before completion. Serious adverse events and responses will also be reviewed by the OSUCCC Data and Safety Monitoring Committee (DSMC). The Co-PIs will also submit a progress report biannually that will be reviewed by the committee per the DSMC plan. All reportable Serious Adverse Events (SAE) will also be reported to the IRB of record as per the policies of the IRB.

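### The closed list that defines a serious adverse event in Section 12.1 can leave out outpatient-managed brain events that Section 11 itself calls serious, so IRB notification and event-level DSMC review are not required for them

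*Protocol*

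**What the plan says.** Section 12.1 of the protocol gives the definition as "Any adverse event that is fatal or life threatening, is permanently disabling, requires inpatient hospitalization or prolongs hospitalization", ending "or results in a congenital anomaly or birth defect". The list is closed and has no item for events that are medically important without meeting one of those outcomes.

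Section 11 (radiation treatment) has a risk list headed "RARE, AND SERIOUS", introduced by "In 100 people receiving radiation therapy, 3 or fewer may have". It names four events: decreased brain function such as motor function, brain swelling ("Swelling of the brain in the treated area which may require steroids"), severe damage to or death of normal brain tissue, and seizure.

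Section 12.3 sets two routes to the IRB. Under 12.3.1 the event is serious in the sense of 12.1. Under 12.3.2 it is not serious but is unexpected, and is related to the study drug, device or research procedure or of unknown association. On timing, "serious adverse events will be reported within 10 days of learning of the event".

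Section 16.7 covers oversight: "Serious adverse events and responses will also be reviewed by the OSUCCC Data and Safety Monitoring Committee (DSMC". The same section provides a biannual progress report to that committee, and review of adverse events by the Co-PIs at meetings held at least monthly.

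**The concern.** The protocol uses the word serious in two senses. Section 11 applies it to four brain injuries by name. Section 12.1 applies it to a list of outcomes that those injuries need not meet. Sections 12.3 and 16.7 follow 12.1, so an event the protocol has already called serious can be handled as non-serious.

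This matters because of the trial's hypothesis. Section 2.0 proposes that ketosis acts together with radiosurgery and protects the brain, and Sections 3.1 and 4 propose that it may make tumours more radiosensitive. Radiation injury to the brain, by arm, is therefore a principal safety question. It is also the class of event that the definition handles least well.

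**Working it through.** **Step 1: the four listed events against 12.1.** Suppose each event is managed without admission, is not life-threatening and is not permanent.

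| Section 11 event | Form that meets no 12.1 criterion | Form that 12.1 does catch |
|---|---|---|
| Decreased brain function | Motor deficit that recovers, no admission | Permanent deficit, or admission |
| Brain swelling | Treated with steroids as an outpatient | Admission, or life-threatening |
| Severe tissue damage or death | Managed without surgery or admission | Surgery, which would normally mean admission |
| Seizure | Self-limited, no admission | Admission, or life-threatening |

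The non-admitted case is foreseen in the protocol. The radionecrosis criteria at the end of Section 17.1 allow the diagnosis to rest on starting steroids and seeing improvement on a repeat scan more than one month later, with no mention of surgery or admission.

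**Step 2: 12.3.1.** This limb needs seriousness as 12.1 defines it. The middle column of the table does not qualify.

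**Step 3: 12.3.2.** This limb needs the event to be unexpected. Section 12.1 calls an event unexpected if its nature, severity or frequency is not identified in the protocol or related documents, or if it is worse than anticipated. The nature of all four is identified in Section 11. At the listed severity and frequency they are not unexpected, and 12.3.2 is not met. The limb also needs a related or unknown association with a study or research procedure. An injury attributed wholly to standard-of-care radiosurgery would fail that too.

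**Step 4: 16.7.** Event-level DSMC review covers serious adverse events and responses. Sections 17.1.1 and 17.1.2 state that radionecrosis does not count as progression, so the responses route is unlikely to show it as a harm.

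**Step 5: scale.** The protocol states no figure that can be reproduced here. The inputs are n = 24 (Section 6.0) and a ceiling of 3 per 100 (Section 11). The lower value of 1 per 100 is an assumption. For one given listed event:

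- Expected cases = 24 × p: 24 × 0.01 = 0.24, and 24 × 0.03 = 0.72.
- Chance of at least one = 1 − (1 − p)^24: 1 − 0.99^24 = 21.4%, and 1 − 0.97^24 = 51.9%.

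These count all cases of that event, including those that 12.1 already catches. They do not measure the gap itself, because the documents do not give the share managed without admission.

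**The case against.** The strongest reply is that other safeguards exist. Section 12.2 requires every adverse event to be documented with its grade and suspected cause. Section 11 requires attribution to both standard therapy and diet. Section 16.7 has the Co-PIs review the frequency and severity of all adverse events, not only serious ones, and gives the DSMC a biannual report. Section 17.0 compares side effects between arms. All of this stands. A reader might infer that these harms bypass the DSMC altogether, or that only admitted or permanently disabled patients are captured. The documents do not support either inference: fatal and life-threatening events are also serious under 12.1, and the DSMC sees the biannual report. What remains is narrower. Co-PI review is done by the investigators, the protocol does not specify the report's safety content, and the arm comparison has no stated interim timing.

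A second reply is that a harmful interaction would appear as excess severity or frequency, and so become unexpected under 12.1. This is partly right. Two cases of one event among 24 is 2/24 = 8.3%, above the listed ceiling. But at a true rate of 3 per 100, two or more cases arise by chance with probability 1 − 0.97^24 − 24 × 0.03 × 0.97^23 = 1 − 0.481 − 0.357 = 16%. Excess frequency is therefore hard to declare in a trial of this size.

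A third reply is that the Section 11 heading is a label in a risk list, not a regulatory classification. That is true, and it is why the point is one of reconciliation.

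Three further inferences go too far:

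- **Pooling the four events.** Without overlap, 4 × 1% to 4 × 3% gives 4% to 12% per patient, and 1 − 0.96^24 = 62% to 1 − 0.88^24 = 95%. Swelling, tissue damage, motor loss and seizure can occur in one patient, and the figure again includes events that 12.1 already captures.
- **The 10-day limit.** Permanence may not be known within it, but the clock runs from learning of the event, and Section 12.2 requires follow-up. An event that later proves permanent can be reported then.
- **Grade 4.** That descriptor includes "prolonged inability to resume usual life pattern", which need not be serious under 12.1. Making every Grade 4 event serious would nevertheless sweep in an unknown number of reports, since abnormal laboratory findings are adverse events (12.1) and chemotherapy is barred only around radiosurgery (7.1.1).

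**Conclusion.** The point holds in limited form. As written, an outpatient-managed event from the Section 11 list, of the listed severity and frequency and neither life-threatening nor permanent, need not be notified to the IRB under either limb of 12.3. It also falls outside the event-level DSMC review in 16.7. Slower or less independent review remains.

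The size cannot be fixed from the documents. The range of 21% to 52% for at least one case of a given listed event among 24 patients rests on assumed rates of 1 to 3 per 100, on the full sample being treated, and on independence between patients. It shows that such events are plausible in this trial, not how many would be missed. The IRB guidelines and the DSMC plan that the protocol refers to are not visible, and they may ask for more than the protocol does. The correction is cheap and should be made.

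**What to change.** 1. In Section 12.1, replace the permanent-disability criterion with one for events that result in persistent or significant disability or incapacity.
2. Add to 12.1 that the four events in the last radiosurgery risk list of Section 11 are processed as serious for 12.3 and 16.7. Sections 11, 12.1, 12.3 and 16.7 would then use the word consistently.
3. Do not extend this to every Grade 4 event.

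The cost is protocol wording and a few more expedited reports, with no new assessment. At the assumed rates the four listed events sum to 4 × 0.24 = 0.96 to 4 × 0.72 = 2.88 expected events in the whole trial. That is an expectation, not a cap, and some of those events would already be reported. The new wording should also say whether a cognitive failure on the Section 9 test battery counts by itself as decreased brain function, because otherwise the number of reports could be larger.

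### Section 12.1 bars any potential alternative cause from the possibly related category, which steers uncertain, timely, non-pattern events towards unrelated and can drop non-serious unexpected ones from IRB notification

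*Protocol*

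**What the plan says.** Protocol section 12.1 names four attribution categories and builds them from timing, pattern of response and alternative cause.

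- *Definitely related*: timely, and "follows a known pattern of response which no alternative cause is present".
- *Probably related*: timely, and "follows a known pattern of response, but which a potential alternative cause may be present".
- *Possibly related*: timely, but the event "follows no known pattern of response, potential alternative cause does not exist".
- *Unrelated*: the lead clause reads "An adverse event for which there is evidence that it is definitely a related cause other than the investigational drug/agent". A second clause adds that in general there is no timely relationship, "or if so, the event does not follow a pattern response and an alternative cause is present".

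Section 12.3 then decides what goes to the IRB. Under 12.3.1 every serious event is notified, with no attribution condition, and the time limit is that "serious adverse events will be reported within 10 days of learning of the event". Under 12.3.2 a non-serious event is notified only if it is unexpected and its "association with the study drug, device, or research-related procedure is either DEFINITELY, PROBABLY, or POSSIBLY RELATED, or UNKNOWN (as defined above". Section 12.2 requires every adverse event to be documented in the medical record together with its suspected cause.

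**The concern.** The categories should weaken step by step from definite to possible. On alternative causes they do not: *probably related* tolerates one, and the weaker *possibly related* forbids one. The category meant for uncertain events is therefore closed to a timely event with no known pattern whenever another explanation is merely conceivable.

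Other explanations are easy to find in this trial. Participants have metastatic cancer and receive radiosurgery, for which section 11 lists headache, tiredness and nausea. They may receive steroids (7.2.1, 7.3.1), and cytotoxic chemotherapy is barred only for three days on either side of radiosurgery (7.1.1). The protocol also says, under Adherence and Retention, that this is the team's first work specifically with cancer patients undergoing radiation therapy. An effect of the diet not previously seen in this setting could well have no known pattern and several potential competing causes.

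What is at stake is whether a non-serious unexpected event of that kind reaches the IRB, because the boundary between *possibly related* and *unrelated* decides that under 12.3.2.

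**Working it through.** No figure is involved. The check is to run every kind of event through the definitions in 12.1 and then through the reporting rule in 12.3.

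**Step 1. Timely events.** Pattern has two levels and alternative cause has three (none, potential, established), so there are 2 × 3 = 6 combinations.

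| Known pattern | Alternative cause | Category under 12.1 |
|---|---|---|
| Yes | None | Definitely related |
| Yes | Potential | Probably related |
| Yes | Established | Unrelated, by its lead clause; not at issue here |
| No | None | Possibly related |
| No | Potential | See step 2 |
| No | Established | Unrelated, by both clauses |

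**Step 2. The remaining combination.** With no known pattern, the event is neither definitely nor probably related. Because a potential alternative cause exists, it is not possibly related. For *unrelated* there are two readings:

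- If a potential cause counts as one that is present, the second clause ("or if so, the event does not follow a pattern response and an alternative cause is present") takes the event in, although no other cause has been established.
- If the lead clause ("An adverse event for which there is evidence that it is definitely a related cause other than the investigational drug/agent") must be met, the event fails it, because nothing definite has been shown. No category then clearly applies.

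The first reading declares an uncertain event unrelated. The second leaves it to the assessor.

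**Step 3. What reporting follows for that combination.**

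- Serious: notified in every case (12.3.1).
- Non-serious and expected: not notifiable under any attribution.
- Non-serious and unexpected: not notifiable under 12.3.2 if called *unrelated*; notifiable if called *unknown*.

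**Step 4. Whether *unknown* is a dependable fallback.** Section 12.3.2 says that this category is defined above. The definition of an adverse event in 12.1 lists four designations (unrelated, definitely, probably, possibly), and *unknown* is neither among them nor defined elsewhere in that section. An assessor who follows 12.1 has no such option.

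**Step 5. Consistency with neighbouring text.** Item d of section 12.2 asks for the suspected cause as possibly or probably related to study treatment, disease progression, concurrent medication, concurrent illness or other factors. Section 11 asks the treating physician to attribute each toxicity to both standard therapy and diet. Both sit most naturally with a scheme in which a possible link to the diet can coexist with a competing cause. The definition of *possibly related* rules that out.

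**The case against.** The best reply is that the scheme has few holes and that the safeguards around it are strong. Much of this stands.

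- A reader might infer that any timely event with another potential cause has no category. The text does not support that. With a known pattern it is *probably related*, and without one the second clause of *unrelated* at least arguably covers it. The main fault is misclassification; a true gap appears only if the lead clause is read strictly.
- A reader might infer that such events go unreported altogether. They do not. Serious events are notified regardless of attribution, all events are documented, and an event treated as *unknown* would be notifiable. The paragraph on time limits in 12.3 also speaks more loosely of non-serious unexpected events that may be associated with the procedure, which an assessor could read as favouring a report. The notification criterion itself, however, is 12.3.2 and runs through the named categories.
- A reader might infer that the side-effect comparison or the removal rules are distorted. Section 17.0 compares side effects between diet groups with no attribution filter. The removal wording in sections 11 and 15 refers to relatedness but does not cite the 12.1 categories.
- A reader might infer that this is the commonest kind of event in the trial, or that *possibly related* will be almost empty. The protocol gives no frequencies, so neither can be claimed.

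None of this explains why the weaker category should carry the stricter condition on alternative causes, or supplies the missing definition of *unknown*.

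**Conclusion.** The definition of *possibly related* is wrong as written. One of the six kinds of timely event, that with no known pattern and a potential but unestablished alternative cause, is either classed as *unrelated* or left ambiguous. The practical effect is confined to IRB notification of events of that kind that are non-serious and unexpected. It arises when the assessor calls them *unrelated*, and nothing in 12.1 offers *unknown* as an alternative. The number of events affected cannot be estimated from the protocol.

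The conclusion rests on reading 12.1 as the source of the categories used in 12.3.2, which the cross-reference in 12.3.2 indicates. It does not extend to the primary endpoints, the planned analyses, serious-event reporting or the removal of participants.

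**What to change.** Three changes of wording, made together:

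1. In 12.1, define *possibly related* as a timely relationship, no known pattern of response, and a potential alternative cause that may be present but is not established.
2. In 12.1, limit *unrelated* to events with an established other cause or with no timely relationship. The second limb is needed: if only an established cause qualified, an untimely event of unclear origin would lose its category.
3. Define *unknown* in 12.1 and add it to the list of designations, or delete it from 12.3.2.

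With these changes the combination in step 2 becomes *possibly related*. A non-pattern event with no alternative cause stays there, the other timely combinations keep their categories, and untimely events are *unrelated*.

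The cost is a short amendment to the reporting definitions and a few more non-serious events sent to the IRB among 24 participants. No assessment, endpoint or analysis changes.
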